#### Open-Label Period (Treatment Cycles 2-4)

For a given subject, the Dysport dose for treatment cycles 2, 3 and 4 will be based on the investigator's judgement (based on efficacy and safety).

- Treatment cycle 2: the Dysport dose can either be the Dysport dose assessed in the previous treatment cycle (double-blind period) for the current cohort or the Dysport dose of the following cohort (provided it has been approved by the DRC).

- Treatment cycles 3 and 4: the Dysport dose can either be the dose assessed in the previous treatment cycle, a lower dose or the dose of the following cohort (provided it has been approved by the DRC).

If any subject fulfils the retreatment criteria and needs a higher dose for treatment prior to the DRC having approved the next dose level, the subject can either accept the dose level currently on, or delay injection until the next dose level is approved by the DRC or withdraw from the study.

A subject can receive up to a maximum of 4 treatment cycles with Dysport. The last treatment cycle should last at least 12 weeks and should not be initiated after Week 36.

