No control of the overall type I error rate is planned as only exploratory descriptive statistics are planned.

2 **SUBJECT POPULATIONS (ANALYSIS SETS)**

Screened population

The screened population is all subjects screened (i.e. who signed the informed consent).

Randomized population

Randomized population is all subjects randomized (i.e. who were randomly allocated to a treatment group).

modified Intent-To-Treat population

The modified Intent-to-Treat (mITT) population is all randomized subjects who received at least one IMP administration and had data for the vaginal dilator induced pain as reported on an 11-point NRS [using the Dilator Maximum Tested Size (DMTS) reported at Baseline] at Baseline and Cycle 1-Week 6 visit (i.e. at least one pain score for one dilator size, which enables an imputed pain score of 10 at DMTS if needed).

The mITT population will be analyzed using subjects as randomized.

Active Treatment Population

The Active Treatment Population is all randomized subjects who received at least one dose of Dysport (including only partial administration) during the DB and/or OL period.

Safety

The safety population is all randomized subjects who received at least one dose of IMP administration (including only partial administration).

The safety population will be analyzed using subjects as treated (i.e. according to actual treatment received).

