3 STATISTICAL METHODS

3.1 Statistical analysis strategy

The statistical analyses will be performed in accordance with the ICH E9 guideline and will be based on the pooled data from the individual study sites, unless otherwise stated.

Medpace will perform the statistical analysis of the efficacy, safety, and antibodies data.

Overall, the analysis strategy is to evaluate safety and efficacy of Dysport compared to Placebo after single administration (DB period), and to evaluate efficacy and safety over repeated Dysport treatments, using analyses by Active Treatment Cycle.

Listings will be presented by subject for DB and OL periods together while the tables associated with the DB period will be separated from the tables assessing repeat treatment with Dysport.

Only descriptive statistics of Stage 1 data will be provided.

Double-Blind Period (Stage 1 Cycle 1) Analyses

For the analysis of the DB period, tables will be displayed using the following treatment group (DB treatment group) labels, in the following order:

- Placebo: placebo groups from all cohorts will be pooled, including for mVPAQ pain, mVPAQ life interference and mFSFI pain domain of cohort 1 despite the change in recall period and time of assessments (see protocol version 3.0).
- Dysport
 - Groups by dose (Dysport 100U, 300U, 400U, 500U, etc.)
 - All Dysport

[figure not shown]
Note: Cohort 1 (100U), 2 (300U), 3 (400U) and 5 (500U) included PVD2 subjects only. Cohort 4 (400U) and 6 (500U) included PVD1 subjects only.

Repeat treatment: Active Treatment Analyses

To assess efficacy and safety data over repeat treatments, data will be analysed using the Active Treatment Cycle approach as described in [Figure 1](#) below. These analyses will be performed on the Active Treatment population:

- for subjects treated with Dysport in the DB period, the first cycle in the DB period will be the first Active Treatment Cycle.
- for subjects treated with placebo in the DB period, the first cycle in the OL period will be the first Active Treatment Cycle.

[Figure 1](#) Active Treatment Cycle Analysis

Three types of summary tables will be produced:

- Summary by number of active treatment cycles: these tables will present the long-term efficacy and safety data with all doses combined, and will display subjects with at least 1 (2, 3 and 4) active treatment cycles.
- Summary by dose received at each active treatment cycle: to evaluate the safety of each dose at a given cycle.

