- Summary over the whole trial (restricted to Week 6 and 12 from DB and from first OL period) by the randomised treatment group (DB treatment group) may be provided for some efficacy analyses.

The type of summary table(s) used for each endpoint are described in sections [3.8](#) and [3.9](#).

Descriptive Statistics

All raw and derived variables will be listed and described using summary statistics. For categorical variables, summary statistics will be displayed by frequency counts and percentages by category. The missing category will be presented if there is at least one missing data in a treatment group. Except otherwise specified, subjects with missing data will be included in the calculation of percentages. For quantitative

variables, summary statistics will be displayed using descriptive statistics by number of observations, mean, standard deviation (SD), median, minimum and maximum.

3.1.1 ***Multiplicity***

No multiple testing will be performed.

3.1.2 ***Significance testing and estimation***

As this is a descriptive safety study, no formal statistical testing will be carried out based on Stage 1 data.

3.1.3 ***Withdrawal visit and end of study visit***

Subjects who have withdrawn early from the study have their last assessment (during early withdrawn visit) mapped as visit 90 in the Study Data Tabulation Model (SDTM). By convention, for these subjects, the visit number will be reassigned to the next empty visit number for analysis (i.e. if a subject has only Visit 1, 2, 3 and 90 entered in the database, the visit number 90 will be reassigned to visit number 4). End of study visits will be described separately as “End of Study (Cycle X)”.

3.2 **Subject disposition and population**

The following disposition summaries and listings will be provided:

- Number and percentages of randomized subjects per country and site by DB treatment group.
- Number and percentages of subjects screened, screen failed and reason for screen failure, randomized, treated, completed, withdrawn and reason for withdrawal by DB treatment group.
- Listing of date of visit.
- Listing of screen failure subjects.
- Listing of withdrawn subjects (on the randomised population).

The following population summaries and listings will be provided:

- Number and percentage of subjects in each analysis population with reasons for exclusion from each population, for the DB treatment group and overall, based on all randomized subjects.
- Listing of randomization details.

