3.8 Efficacy analysis

The efficacy endpoints will be summarized using the analysis strategy in Section 3.1. Descriptive statistics will be provided for:

- the DB period, by DB treatment group for the mITT population.
- the Active Treatment Cycle, on the Active Treatment population: by number of active treatment cycles (all doses combined and/or by dose). The mITT population will be the primary population for analysis of efficacy data. Week 6 and Week 12 will be the timepoints of primary interest.

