3.8.2 Secondary efficacy analyses

Vestibular pain using a vaginal dilator

A set of 8 vaginal dilators of increasing diameter (#1 being the smallest and #8 being the largest) will be used to provoke pain to allow assessment of the vestibular pain intensity in each subject. Subjects will be required to rate the pain for each dilator size on an 11-point NRS at each visit. Pain score will be entered by the investigator (or delegated site staff) in the eCRF.

Based on the subjective pain threshold, the largest sized dilator that the subject accepts to test, will be defined as the Dilator Maximum Tested Size (DMTS) that will be established at the Baseline Visit. The dilator test will be used to assess the change from Baseline in the vaginal dilator induced pain as reported on an NRS (using the DMTS reported at baseline) as well as the dilator size that provokes maximum pain. If a dilator size is not tested due to pain intensity, the pain will be scored at 10. If the test is not done due to other reasons, then the pain score will be considered as missing. Endpoints and corresponding analyses are described in [Table 1](#).

Table 1 Dilator Induced Pain - Endpoints and Corresponding Analyses

Endpoint	Analyses
Mean change from Baseline to each post-treatment visit in the vaginal dilator induced pain as reported on the 11-point NRS[1]	
Convention:
 
According to the mITT Population definition, there will be no missing data for Week 6. For Week 12, the missing values will be kept as missing.
 
- descriptive statistics: actual values and change from baseline values will be presented at all timepoints (over the double-blind and open-label periods). A plot of mean changes over time from baseline in pain scores will be provided by treatment group for DB period.
 
Active Treatment Cycle:
 
 - A summary by number of active treatment cycles. - A plot of mean changes over time from baseline in pain scores will be provided by randomized treatment group for Week 6 and Week 12 over both of the DB and first OL period.
Proportion of subjects who reported at least a 50% decrease in vaginal dilator induced pain as reported on the 11-point NRS[1] at each post-treatment	
Convention:
 
According to the mITT Population definition, there will be no missing data for Week 6. For Week 12, the missing values will be kept as missing.
 
- descriptive statistics will be presented at all timepoints.

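### The SAP's plot of pain change by randomised group across the double-blind and first open-label periods, as placed, keeps a placebo subject's double-blind values only if she later received open-label Dysport

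*SAP*

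**What the plan says.** SAP 3.8.2, Table 1, specifies two plots for dilator-induced pain at the baseline maximum tested size. One covers the double-blind period by treatment group. The other is listed under the Active Treatment Cycle heading and "will be provided by randomized treatment group for Week 6 and Week 12 over both of the DB and first OL period".

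SAP 3.1, in its part on repeat treatment, states: "These analyses will be performed on the Active Treatment population". It then lists three types of output for those analyses. The third is a "Summary over the whole trial (restricted to Week 6 and 12 from DB and from first OL period) by the randomised treatment group", described as optional. SAP 3.8 repeats the assignment for efficacy: "the Active Treatment Cycle, on the Active Treatment population: by number of active treatment cycles (all doses combined and/or by dose". It puts the double-blind efficacy outputs on mITT.

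SAP Section 2 defines the set, counting a dose in either period: "The Active Treatment Population is all randomized subjects who received at least one dose of Dysport (including only partial administration) during the DB and/or OL". For placebo subjects SAP 3.1 adds: "for subjects treated with placebo in the DB period, the first cycle in the OL period will be the first Active Treatment Cycle".

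On the second-cycle dose in Stage 1, Protocol 3.7.2.1 states: "the Dysport dose can either be the Dysport dose assessed in the previous treatment cycle (double-blind period) for the current cohort or the Dysport dose". The sentence goes on to name the next cohort's dose, once the Data Review Committee (DRC) has cleared it.

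**The concern.** The plot shows randomised groups at double-blind Week 6 and Week 12, so a reader will take those points as the randomised comparison. On the Active Treatment population they are not. Whether a placebo subject's double-blind value appears depends on something that happens at Week 12 or later, namely whether she goes on to open-label Dysport. Dysport-randomised subjects face no such condition. If taking open-label treatment is related to earlier response, the placebo line shifts and the Dysport lines do not. The same visits may also show a different placebo mean and n from the mITT double-blind plot, with no stated reason.

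The open-label half raises a separate reading problem. In every group it contains only retreated subjects. Lines carry the randomised dose, but for groups randomised below 500 U the first open-label injection may have been at the next cohort's dose. A step between the two halves can therefore come from a change of subjects or of dose rather than from repeat treatment.

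**Working it through.** The plan states no figure for this point, so the check is a logical one followed by an illustration.

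**1. Which population applies.** The plot line itself names none. Its heading (Active Treatment Cycle), the population sentence in SAP 3.1 and the assignment in SAP 3.8 all lead to the Active Treatment population. SAP 3.1 also lists a display of the same shape (by randomised group, Weeks 6 and 12, double-blind plus first open-label period) among the repeat-treatment outputs. Nothing assigns this plot elsewhere.

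**2. Who qualifies.**
- Randomised to Dysport and dosed: qualifies on Day 1, even after a partial dose.
- Randomised to placebo: qualifies only after an open-label Dysport injection. Protocol 3.7.3 makes that conditional on the investigator's judgement, the subject's willingness, no unacceptable adverse event, a 12-week interval and negative pregnancy and drug tests. Footnote b to Protocol Table 2 shows that a subject can finish at Week 36 without it.

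**3. Planned sizes, cohorts 1 to 6** (Protocol 3.1.1; SAP 1.3.5 for the cohorts analysed).
- Placebo: 6 cohorts × 2 = 12, pooled into one line (SAP 3.1).
- Dysport: 8 + 8 + 8 + 6 + 8 + 8 = 46. Total: 12 + 46 = 58.
- Check of the counting over all 12 cohorts: 7 × 10 + 8 + 4 × 10 = 118, which matches the protocol's Stage 1 maximum.
- Let k be the number of placebo subjects who never receive open-label Dysport. The double-blind placebo points then rest on at most 12 − k subjects. Each omission removes 1/12 = 8.3% of the placebo line and nothing from the Dysport lines.

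**4. Illustration of size.** Assume placebo changes are Normal with mean -2 and SD 3, the Stage 2 planning values in Protocol 11.2. Draw 12 values, drop k, and average the remaining 12 − k; repeat 200,000 times. The expected plotted placebo mean is:

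| k | Unrelated to response | Best responders omitted | Correlation 0.5 between poor response and retreatment | Worst responders omitted |
|---|---|---|---|---|
| 0 | -2.00 | -2.00 | -2.00 | -2.00 |
| 1 | -2.00 | -1.56 | -1.78 | -2.44 |
| 2 | -2.00 | -1.18 | -1.59 | -2.82 |
| 3 | -2.00 | -0.82 | -1.41 | -3.18 |
| 4 | -2.00 | -0.47 | -1.24 | -3.53 |

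The shift for k = 1 is -1.56 − (-2) = 0.44 points, and for k = 3 it is -0.82 − (-2) = 1.18 points. Shifts of the same size arise in the other direction if the worst responders are the ones omitted. The best-responder and worst-responder columns are extremes.

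**5. Dose in the open-label half.** The cohort doses are 100, 300, 400 and 500 U. Under the rule in Protocol 3.7.2.1, subjects in the 100, 300 and 400 U groups (planned 8 + 8 + 14 = 30) could move to the next cohort's dose. The DRC recommendation reported in SAP 1.3.5 found no reason to go higher after cohorts 1 to 6, so the 500 U group (planned 16) had no higher approved dose to move to.

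**The case against.** **The population is inferred.** The plot line names no analysis set. SAP 3.8 ties the Active Treatment population to summaries by number of cycles or by dose, and this plot is neither. SAP 3.8 also names mITT as the main efficacy set, and the same Table 1 cell uses an mITT missing-data convention. This is fair as far as it goes. But none of it clearly moves an output listed under Active Treatment Cycle to another set, and if mITT was intended the SAP needs to say so. Either reading calls for a wording change.

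**Little depends on the figure.** This stands. The analysis is descriptive with no testing, and double-blind efficacy has its own mITT plot and tables. The DRC advised against using Stage 1 to assess efficacy. The whole-trial summary is optional, and the endpoint tables in SAP 3.8 do not call for it.

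**The number omitted may be near zero.** This also stands as a possibility. Protocol 3.7.3 offers open-label Dysport to every subject willing to continue and sets no pain or response threshold.

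**Stronger readings to resist.** A reader might infer that the plot will favour Dysport. The documents do not support a direction: subjects who do well may see no need for retreatment, but subjects who do poorly may withdraw, and Protocol 3.7.2.1 lists withdrawal as an option for someone waiting for a dose not yet approved. A reader might also infer that the trial's randomised comparison is compromised, or that the dose can rise within every Dysport line. The first fails because the mITT double-blind outputs are separate; the second fails for 500 U.

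**Conclusion.** As the SAP is written, the double-blind placebo points of this one plot are selected on later open-label treatment and the double-blind Dysport points are not. That follows from the population definition and does not depend on any assumed number. The size does: with 12 planned placebo subjects and the planning values of -2 and SD 3, the expected placebo mean would lie between about -1.56 and -2.44 if one subject is omitted and between about -0.82 and -3.18 if three are. It is unchanged if none is omitted or if omission is unrelated to response. These figures assume Normal changes, ignore the bounds of the 0 to 10 scale, and borrow Stage 2 planning values for Stage 1. The number of placebo subjects never given open-label Dysport, and how they responded, are not in the documents. The consequence is limited to this descriptive figure and to any whole-trial summary by randomised group that is actually produced.

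**What to change.** In SAP 3.1 and Table 1:
- State that the double-blind points of this plot, and of any whole-trial summary by randomised group that is produced, use the mITT population by randomised group. All placebo subjects meeting the mITT definition are then included whether or not they are retreated.
- Show n for each group at each timepoint.
- Label the open-label points as retreated subjects only, with a note that the dose received may differ from the randomised dose. SAP 3.9.1 already plans a table of actual dose per cycle by double-blind group, which the note can cite.

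Splitting the open-label half into panels by dose received is a presentation choice and is not needed; the groups are too small for it to help much.

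The cost is a wording change and one reprogrammed figure, with no new data. The downside is that the double-blind and open-label parts of the figure will have different n, which the displayed counts make visible.

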--------------------------------	--

Frequency of intercourse and pain during intercourse

Cohort 1: Each day during the Screening period (Day -14 to Day 1), and during the month (28 days) preceding the next planned visit, subjects are to record in the eDiary if they had intercourse, the number of intercourse instances, corresponding pain during each intercourse instance (using an 11-point NRS) and details of pain rescue medication, if taken, to prevent or treat vestibular pain.

Cohort 2 onwards: Each day during the Screening period and during the 2-week period preceding the next planned visit, subjects are to record if they had intercourse, the number of intercourse instances, corresponding pain during each intercourse instance on an 11-point NRS and details of pain rescue medication, if taken, to prevent or treat vestibular pain.

Intercourse diary entry with no intercourse in the previous 24 hours and pain score entered as 0 will be considered as no intercourse in the previous 24 hours. Entry with no intercourse in the previous 24 hours and pain score different from 0 will be considered as an intercourse entry with the entered pain score.

Endpoints and corresponding analyses are described in [Table 3](#).

Table 3 Intercourse - Endpoints and Corresponding Analyses

Endpoint	Analyses
Mean change from baseline to each post-treatment visit in the pain during intercourse as reported on the 11-point NRS	
Conventions: Analysis of pain will be done on the subjects who had intercourse in the corresponding period.
 
Average pain score over the week preceding the visit: The weekly average will be calculated as the average of the score over the last week (7 days) prior to the visit, for all cohorts (including cohort 1). The weekly average will be calculated if at least 1 pain score has been recorded over the considered week.
 
Average pain score over the 2 weeks preceding the visit: The 2-week average will be calculated as the average of the score over the last 2 weeks (14 days) prior to the visit, for all cohorts (including cohort 1). The 2-week average will be calculated if at least 1 pain score has been recorded in the considered 2-week period.

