	
 - descriptive statistics: actual values and change from baseline values will be presented at all timepoints. In the same table, number of subjects with or without partner at each timepoint will be also presented. 
Active Treatment Cycle:
 
 - A summary by number of active treatment cycles will be used.
Mean change from baseline to each post-treatment visit in the number of intercourse instances in subjects with partners	
Conventions:
 
Analysis will be done on the subjects who have a partner at baseline and at the specific visit (DB Week 6, or Week 12).
 
Number of intercourse instances over the week preceding the visit
 
The number of intercourse instances over the week preceding the visit will be calculated as the total number of intercourse instances over 7 days prior to the visit. There should be at least 1 eDiary input recorded in the week for calculating the number of intercourse instances over the period, otherwise it will be considered missing.
 
Number of intercourse instances over the 2 weeks preceding the visit
 
The number of intercourse instances over the 2 weeks preceding the visit will be calculated as the total recorded number of intercourse instances over 14 days prior to the visit. There should be at least 1 eDiary input recorded in the period for calculating the number of intercourse instances over the period, otherwise it will be considered missing.
 
 - descriptive statistics: actual values and change from baseline values will be presented at all timepoints. 
Active treatment cycle:
 
 - A summary by number of active treatment cycles will be used.
Proportion of subjects having taken pain rescue medication associated with intercourse	
 - descriptive statistics: number and percentage of subjects using pain rescue medication within the 1-week/2-week period preceding each visit, in subjects with non-missing pain score value in the corresponding period. 
Active Treatment Cycle:
 
 - A summary by number of active treatment cycles will be used.

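### The intercourse count is an unscaled total accepted with one diary entry in 7 or 14 days, so change from baseline mixes true frequency with diary completion

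*SAP*

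**What the plan says.** The endpoint, in SAP 3.8.2, Table 3, is "Mean change from baseline to each post-treatment visit in the number of intercourse instances in subjects with partners". Two versions are derived.

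- The 7-day count is "calculated as the total number of intercourse instances over 7 days prior to the visit", with the condition "There should be at least 1 eDiary input recorded in the week for calculating the number of intercourse instances over the period".
- The 14-day count is "calculated as the total recorded number of intercourse instances over 14 days prior to the visit", with the condition "There should be at least 1 eDiary input recorded in the period for calculating the number of intercourse instances over the period".

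If the condition fails, "otherwise it will be considered missing". A count is therefore missing only when the window holds no entry at all.

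From Cohort 2 onwards the diary is due "Each day during the Screening period and during the 2-week period preceding the next planned visit". Protocol 7.4.2.2 gives each entry a 24-hour recall, so the next day's entry does not recover a skipped day. SAP 3.8.2 says how to read an entry that reports no intercourse. It has no rule for a day without an entry.

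SAP 3.10.1 sets minimum numbers of valid items for the mVPAQ, mFSFI and PHQ-9 and rescales partly missing scores. It has no counterpart for this diary. SAP 3.7 covers compliance with drug administration only. Protocol 11.4.5 promises missing-data sensitivity analyses where appropriate, and the SAP specifies none for this endpoint.

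**The concern.** A sum over a fixed window measures frequency only if every day in the window was observed. Here the sum is taken over whichever days were recorded and compared with a baseline sum taken the same way. If the number of recorded days differs between baseline and a later visit, the change moves even when behaviour does not. A reader of the table could not tell less intercourse from fewer diary entries, because no summary of diary days is planned.

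The companion endpoint, pain during intercourse, is a mean of recorded scores and does not have this arithmetic fault. The fault is specific to the count.

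The groups are small. By the planned allocation, Cohorts 1 to 6 give 46 Dysport subjects (8 in each of five cohorts and 6 in Cohort 4) and 12 pooled placebo subjects (2 in each of six). They are then restricted to those with a partner at baseline and at the visit. A few sparse diaries can move a group mean.

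**Working it through.** The documents state no expected count, diary completion or power for this endpoint, so there is no planned figure to reproduce. The check takes the derivation rule and asks what it returns when true frequency does not change.

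**Inputs from the documents.** The window D is 7 or 14 days, the minimum is 1 entry, entries are daily with 24-hour recall, and the screening window is Day -28 to Day -11 (Protocol 5.2.1.1).

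**Assumed inputs.** True frequency m per window, completion c (the share of days with an entry), and missed days having the same intercourse rate as recorded days.

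**Minimum data accepted.** 1/7 = 14.3% of days, or 1/14 = 7.1%. With one recorded day at a true 2 per 14 days, the expected count is 2 x 1/14 = 0.14.

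**Expected raw total.** Given at least one entry, it is m x c / (1 - (1 - c)^D). For D = 14 the denominator is practically 1 at the values used here, so the false change is close to m x (c_later - c_baseline).

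| True count per 14 days | Completion | False change |
|---|---|---|
| 2 | 90% to 75% | 2 x (0.75 - 0.90) = -0.3 |
| 2 | 90% to 60% | 2 x (0.60 - 0.90) = -0.6 |
| 3 | 90% to 60% | 3 x (0.60 - 0.90) = -0.9 |
| 2 | 90% to 90% | 0 (level understated by 10%) |
| 2 | 70% to 90% | 2 x (0.90 - 0.70) = +0.4 |

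**Rate per recorded day.** In a simulation of 200,000 subjects per setting, with days missed at random and a true 2 per 14 days, the raw 14-day mean was 1.80, 1.40 and 1.00 at 90%, 70% and 50% completion. The prorated mean was 2.00 at all three.

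**Between groups.** If two groups have the same true frequency and the same completion at each visit, both show the same false change and it cancels in the difference. It does not cancel if completion differs by group, and the sign then depends on which group and which visit.

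**Short baseline with perfect compliance.** Screening on Day -11 leaves about 11 possible diary days before Day 1, against 14 before a later visit. The apparent ratio is 14/11 = 1.27, a rise of up to 27%. At a true 2 per 14 days the baseline total is 2 x 11/14 = 1.57, so the false change is +0.43. Only the 14-day count is affected, and only in subjects screened fewer than 14 days before baseline.

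**Cost of a half-days minimum.** At 60% random completion, P(at least 7 of 14) = 0.85 and P(at least 4 of 7) = 0.71. About 15% of subjects (14-day) or 29% (7-day) would become missing at that visit.

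**The case against.** The strongest reply is that little rests on this number. The study ended before Stage 2, and the DRC advised against using Stage 1 to assess efficacy (SAP 1.3.5). The SAP plans descriptive statistics only, with no formal testing (3.1.2). The SAP also undertakes to list raw variables, so sparse diaries could be found subject by subject. All of this stands and limits severity. It does not make the displayed mean right, and a listing does not replace a summary of diary days.

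The second reply concerns the missed days. If subjects open the diary mainly when they have had intercourse, the raw total is nearly correct and a prorated rate is too high. Two instances logged on 7 recorded days would become 2/7 x 14 = 4, double the truth. The documents do not show which pattern holds. This stands, and it is why the raw total should remain visible.

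Three stronger readings are tempting, and the documents do not support them.

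- A reader might infer that the SAP scores a missed day as no intercourse. It contains no such rule. The zero is the arithmetic effect of an unscaled sum.
- A reader might infer that the endpoint is biased toward a decrease. The sign depends on whether completion falls or rises, and the short baseline window pushes the other way.
- A reader might infer that the comparison of Dysport with placebo is biased. That needs completion to differ by group, and no completion data are given.

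**Conclusion.** The concern holds as a flaw in the derivation rule. Followed as written, Table 3 returns a change that combines intercourse frequency with diary completion, and no other part of the SAP corrects or displays this.

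The false rise of up to 27% in the 14-day count follows from the permitted screening window alone, for a subject screened at Day -11. The other sizes, such as -0.6 for completion falling from 90% to 60% at a true 2 per 14 days, are illustrations. They rest on assumed frequency and completion, and on missed days resembling recorded ones. The mechanism is certain; its size and sign in this trial are unknown.

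The point merits a correction to the SAP, but nothing larger depends on it. The endpoint is secondary and descriptive, and no dose selection for Stage 2 remains to be made from it.

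**What to change.** 1. Derive the count as (instances recorded / diary days recorded) x 7 or x 14. This also removes the effect of a short baseline window.
2. Keep the raw total beside it as a sensitivity summary. Close agreement would show that the handling of missed days matters little.
3. Tabulate diary days recorded by visit and treatment group, for the 7-day and 14-day windows.
4. If a minimum number of days is wanted, set it before unblinding and report how many subjects it removes. A half-days rule could remove the 15% or 29% calculated above, which is substantial with at most about 12 placebo subjects by the planned allocation. The documents give no basis for a particular cutoff.
5. State in the SAP that proration assumes unrecorded days resemble recorded ones, and that it overstates frequency if subjects mainly log days with intercourse.

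The cost is SAP wording, a small derivation change and one extra table, all from data already collected. With very few entries a prorated value is unstable, so the table of diary days should be read alongside it.
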